Grade 4 Neutropenia (ANC of $< 0.5 \times 10^9/L$) OR Occurrence of neutropenic fever or infection	
 • Monitor with complete blood count at least every 2 weeks • Strongly recommend initiation of growth factors and other supportive care including antibiotic prophylaxis 	Withhold study drug	
 • On resolution to a lower grade or baseline (ANC of $\geq 1 \times 10^9/L$), resume at the same dose level or at the next lower dose level at the discretion of the investigator (also refer to treatment guidelines for infection) • In case of recurrence after restarting treatment, resume at the next lower dose level

ANC = absolute neutrophil count; CTCAE = Common Terminology Criteria for Adverse Events.

Table 11 Dose Modification/Toxicity Management Recommendations for Thrombocytopenia

Adverse Reaction CTCAE v5.0 Grade/Severity	Recommended Management	Recommended Dosing Modification	Recommended Follow-up
Grade ≤3 Thrombocytopenia without bleeding (Platelet count > 25 × 10 ⁹ /L)	
 If persistent, consider supportive care as needed 	Continue current dose	
 In case of bleeding or worsening, manage as next higher grade
Grade 4 Thrombocytopenia (Platelet count < 25 × 10 ⁹ /L) OR Any grade thrombocytopenia with bleeding	
 Monitor with complete blood count at least every 2 weeks Consider supportive care including platelet transfusion (as clinically indicated) On resolution to a lower grade or baseline, resume at the same dose level 	Withhold study drug	
 In case of recurrence after restarting treatment, consider next lower dose level at the discretion of the investigator

CTCAE = Common Terminology Criteria for Adverse Events.

Table 12 Dose Modification/Toxicity Management Recommendations for Anemia

Adverse Reaction CTCAE v5.0 Grade/Severity	Recommended Management	Recommended Dosing Modification	Recommended Follow-up
Grade 3 Anemia (Hemoglobin < 8.0 g/dL; < 4.9 mmol/L; < 80 g/L)	
 Transfusion is indicated, especially if symptomatic 	Withhold study drug	
 On resolution to ≤Grade 2 or baseline, resume at the same dose level or at the next lower dose level at the discretion of the investigator In case of recurrence after restarting treatment, resume at the next lower dose level
Grade 4 Anemia (Life-threatening consequences; urgent intervention indicated)	
 Transfusion urgently indicated Monitor with complete blood count at least every 2 weeks 	Withhold study drug	
 On resolution to ≤Grade 2 or baseline, resume at the next lower dose level at the discretion of the investigator In case of recurrence after restarting treatment, consider next lower dose level at the discretion of the investigator

CTCAE = Common Terminology Criteria for Adverse Events.

Table 13 Dose Modification/Toxicity Management Recommendations for Rash and Cutaneous Skin Reactions

Adverse Reaction CTCAE v5.0 Grade/Severity	Recommended Management	Recommended Dosing Modification	Recommended Follow-up
Grade 1 or 2 Rash or Cutaneous Reactions (Covering < 30% of BSA, with no evidence of superinfection)	
 Initiate supportive treatment with emollients, antihistamines (for pruritus), or topical steroids Counsel patients to avoid skin irritants Monitor closely for any worsening 	Continue current dose	
 In case of worsening, treat as Grade 3 or 4
Grade 3 Rash or Cutaneous Reactions (Covering > 30% BSA, moderate/severe symptoms, associated with local superinfection)	
 Initiate supportive treatment with emollients, antihistamines (for pruritus), or topical steroids If rash does not resolve with topical steroids, consider low-dose systemic steroids (0.5 to 1 mg/kg/day methylprednisolone IV or oral equivalent per institutional guidelines) Monitor closely for any worsening Consider skin biopsy and dermatology consult 	Withhold study drug	
 If resolved in less than 28 days, resume study drug at the same or a reduced dose as per investigator's discretion If not resolved within 28 days after dose reduction, permanently discontinue study drug. Treat as the next higher grade
Grade ≥ 4 (Life threatening) OR Any grade of SJS, TENS, or DRESS	
 Obtain skin biopsy and dermatology consult Treat as per the diagnosis and standard treatment guidelines (such as IV antibiotics and IV steroids) 	Permanently discontinue study drug	
 Continue close follow-up until resolution If improves to baseline, gradually taper steroids as per local standard

BSA = body surface area; CTCAE = Common Terminology Criteria for Adverse Events; DRESS = drug reaction with eosinophilia and systemic symptoms; IV = intravenous; SJS = Steven's Johnsons' Syndrome; TENS = toxic epidermal necrolysis.

Table 14 Dose Modification/Toxicity Management Recommendations for Nausea/Vomiting

Adverse Reaction CTCAE v5.0 Grade/Severity	Recommended Management	Recommended Dosing Modification	Recommended Follow-up
Grade 1 or 2 Nausea or vomiting	
 • Initiate dietary modification (small frequent meals, bland foods, sipping/eating slowly) • Initiate antiemetic therapy as needed 	Continue current dose	
 • Reassess within 48 hours of starting supportive treatment • If responsive to antiemetic treatment: 
 ○ No change in study drug dose ○ Monitor as clinically indicated until complete resolution • If not responsive to antiemetic treatment or worsening 
 ○ Withhold study drug ○ In case of worsening, treat as Grade 3 or 4
Grade 3 Nausea or vomiting	
 • Initiate antiemetic therapy • IV hydration • Consider hospitalization • If persistent despite maximal supportive care and dose hold, investigate other causes (consider GI consult, imaging, CNS imaging) 	Withhold study drug	
 • If resolved in less than 28 days, resume study drug at the same or a reduced dose as per investigator’s discretion • If not resolved within 28 days, resume study drug at reduced dose • Consider using scheduled antiemetic prior to HMPL-523 administration for prophylaxis
Grade ≥ 4 Vomiting	
 • Initiate antiemetic therapy IV • IV hydration • Hospitalization for stabilization/management • If persistent despite maximal supportive care and dose hold, investigate other causes (consider GI consult, imaging, CNS imaging) 	Withhold study drug	
 • If resolved in less than 28 days, resume study drug at the same or a reduced dose as per investigator’s discretion • If not resolved within 28 days, resume study drug at reduced dose • Consider using scheduled antiemetic prior to HMPL-523 administration for prophylaxis

CTCAE = Common Terminology Criteria for Adverse Events; CNS = central nervous system; GI = gastroenterology; IV = intravenous.

APPENDIX 16 PROHIBITED CONCOMITANT MEDICATIONS THAT HAVE A KNOWN RISK OF QT PROLONGATION AND/OR TORSADES DE POINTES (TDP)

Generic Name	Brand Names (Partial List)	Drug Class
Aclarubicin	Aclacin and others	Anticancer
Amiodarone	Cordarone, Pacerone, Nexterone	Antiarrhythmic
Anagrelide	Agrylin, Xagrid	Phosphodiesterase 3 inhibitor
Arsenic trioxide	Trisenox	Anticancer
Astemizole	Hismanal	Antihistamine
Azithromycin	Zithromax, Zmax	Antibiotic
Bepriidil	Vascor	Antihypertensive
Cesium Chloride	Energy Catalyst	Unclassified
Chloroquine	Aralen	Antimalarial
Chlorpromazine	Thorazine, Largactil, Megaphen	Antipsychotic / Antiemetic
Chlorprothixene	Truxal	Antipsychotic
Cilostazol	Pletal	Phosphodiesterase 3 inhibitor
Ciprofloxacin	Cipro, Cipro-XR, Neofloxin	Antibiotic
Cisapride	Propulsid	Gastroprokinetic agent
Citalopram	Celexa, Cipramil	Antidepressant, SSRI
Clarithromycin	Biaxin, Prevpac	Antibiotic
Cocaine	None	Local anesthetic
Disopyramide	Norpace	Antiarrhythmic
Dofetilide	Tikosyn	Antiarrhythmic
Domperidone	Motilium, Motillium, Motinorm Costi, Nomit	Antinausea
Donepezil	Aricept	Cholinesterase inhibitor
Dronedarone	Multaq	Antiarrhythmic

Generic Name	Brand Names (Partial List)	Drug Class
Droperidol	Inapsine, Droleptan, Dridol, Xomolix	Antipsychotic/Antiemetic
Erythromycin	E.E.S and others	Antibiotic
Escitalopram	Cipralext, Lexapro, Nexito,	Antidepressant, SSRI
Flecainide	Tambocor, Almarytm, Apocard, Ecrinal, Flécaïne	Antiarrhythmic
Fluconazole	Diflucan, Trican	Antifungal
Gatifloxacin	Tequin	Antibiotic
Grepafloxacin	Raxar	Antibiotic
Halofantrine	Halfan	Antimalarial
Haloperidol	Haldol	Antipsychotic
Hydroquinidine	Serecor	Antiarrhythmic
Hydroxychloroquine	Plaquenil and others	Antimalarial
Ibogaine	None	Psychedelic
Ibutilide	Corvert	Antiarrhythmic
Levofloxacin	Levaquin, Tavanic	Antibiotic
Levomepromazine (Methotrimeprazine)	Nosinan and others	Antipsychotic
Levomethadyl acetate	Orlaam	Opioid agonist
Levosulpiride	Neoprad, Lesuride and others	Antipsychotic, prokinetic agent
Meglumine antimoniate	Glucantime	Antileishmanial
Mesoridazine	Serentil	Antipsychotic
Methadone	Dolophine, Symoron, Amidone, Methadose, Physeptone, Heptadon	Opioid agonist
Mobocertinib	Exkivity	Anticancer
Moxifloxacin	Avelox, Avalox, Avelon	Antibiotic

Generic Name	Brand Names (Partial List)	Drug Class
Nifekalant	Shinbit	Antiarrhythmic
Ondansetron	Zofran, Anset, Ondemet, Zuplenz, Emetron, Ondavell, Emeset, Ondisolv, Setronax	Antiemetic
Oxaliplatin	Eloxatin	Antineoplastic agent
Papaverine	Multiple	Antispasmodic
Pentamidine	Pentam	Antifungal
Pimozide	Orap	Antipsychotic
Probucol	Lorelco	Antihyperlipidemic
Procainamide	Pronestyl, Procan	Antiarrhythmic
Propofol	Diprivan, Propoven	Anesthetic, general
Quinidine	Quinaglute, Duraquin, Quinact, Quinidex, Cin-Quin, Quinora	Antiarrhythmic
Roxithromycin	Rulide and others	Antibiotic
Sertindole	Serdolect and others	Antipsychotic
Sevoflurane	Ultane, Sojourn	Anesthetic, general
Sotalol	Betapace, Sotalex, Sotacor	Antiarrhythmic
Sparfloxacin	Zagam	Antibiotic
Sulpiride	Dogmatil and others	Antipsychotic
Sultopride	Barnetil, Topral and others	Antipsychotic
Terfenadine	Seldane	Antihistamine
Terlipressin	Teripress and others	Vasoactive agent
Terodiline	Micturin and others	Antispasmodic
Thioridazine	Mellaril, Novoridazine, Thioril	Antipsychotic
Vandetanib	Caprelsa	Anticancer

APPENDIX 17 EUROPEAN UNION GENERAL DATA PROTECTION REGULATION- AND CLINICAL TRIAL REGULATION- COMPLIANT DATA PROTECTION

HUTCHMED Limited, as Data Controller of this study, ensures that all processing activities involving personal data performed in the scope of the study comply with applicable privacy and data protection laws, including, but not limited to, Regulation (EU) 2016/679 (General Data Protection Regulation), together “Data Protection Laws.”

HUTCHMED Limited will ensure that the technical, organizational, and contractual security measures described below are periodically reviewed and updated to take into account relevant technological developments and/or changes to the processing of personal data in conjunction with the study. All locations, personnel, and information systems that are used to perform services for the study will be covered by the measures described in this appendix.

HUTCHMED Limited may apply additional statutory measures where required by the national laws that apply to the study or that HUTCHMED Limited otherwise deems appropriate, and in such cases, it will implement these measures even if they are not expressly listed below.

Technical Measures

- Restriction and monitoring of physical access to the offices and information processing facilities to employees, personnel, and approved visitors
- Ensuring appropriate and restricted user access relevant to the function and type of activity performed in relation to the study (“role-based access”)
- The pseudonymization and encryption of personal data, as appropriate
- Processing personal information in accordance with the data minimization principle, meaning that personal data is never collected “just in case” and each data element collected is necessary for the purpose of conducting the study
- The ability to ensure the ongoing confidentiality, integrity, availability, and resilience of processing systems and services
- Network, application, and database security by means of firewalls and antivirus/antimalware
- Ensuring the detection of malware purposed for unauthorized deletion, blocking, copying of information, or disabling security measures
- The means to restore the availability and access to personal information in a timely manner in the event of a physical or technical incident
- Logging of security events/incidents in information systems and implementation of system audit trails, where applicable
- Ensuring that information systems, computers, and software involved in the performance of the services provided in the study are backed up
- A process for regularly testing, assessing, and evaluating the effectiveness of technical measures

- Procedures to detect any personal data breach that may occur

Study subjects will be assigned a subject identification number for the purposes of transferring their personal data, and names or other information that would make study subjects directly identifiable will not be transferred. The information technology systems used to collect, process, and store study-related data are secured by the technical, organizational, and contractual security measures described in this appendix, in particular so that identifiable personal data of study subjects are not processed other than as contemplated by the protocol.

Sponsor representatives acting on behalf of HUTCHMED Limited will have read-only access to fully identifiable personal data only when strictly necessary, eg, in the scope of the on-site monitoring visits and audits, only for the source data verification mandatory under the clinical study framework, including the ICH-GCP obligations applicable to the conduct of the study.

In addition, records containing fully identifiable personal data may be reviewed by national and international regulatory authorities.

Organizational Measures

HUTCHMED Limited has implemented and maintains the following organizational measures:

- The provision of information notices to, and where required, obtaining consent from, data subjects (including the participants in the study)
- Procedures and practices for data protection compliance, including policies and standard operating procedures relating to personal data security, data subject rights requests, data retention, personal data breaches, vendor contracting, and transfer impact assessments
- Procedures and practices for securing the destruction of paper documents containing personal data after the applicable retention period, if any
- Procedures and practices that cover reporting, analysis, monitoring, and resolution of security incidents
- Business continuity procedures and practices to help ensure that HUTCHMED Limited can continue to provide services through operational interruption
- Processes to ensure that cross-border transfers of personal data comply with the Data Protection Laws
- Procedures and practices for employee and staff awareness and training
- Procedures and practices for auditing compliance with the Data Protection Laws

Contractual Measures

When selecting vendors, HUTCHMED Limited has due diligence processes in place. In addition to the above-mentioned technical and organizational measures, HUTCHMED Limited, by means of internal measures and imposing contractual data processing clauses on relevant subcontractors and third parties, ensures the confidentiality of records and personal data of study subjects. In addition, the contracts between the Sponsor and study sites specify the responsibilities of the parties relating to data protection, including the handling of personal data breaches, respective communication, and cooperation of the parties.

Personal Data Breaches

HUTCHMED Limited has put in place a process to assess and, if required, report personal data breaches occurring at its or its subcontractors' facilities and premises. In the event of a data breach, HUTCHMED Limited will apply appropriate measures to mitigate the risks to data subjects based on the specific context of the data breach and taking into account the rights and freedoms of the individuals. If a breach is likely to result in a risk to data subjects, HUTCHMED Limited will determine whether it is required to notify the applicable supervisory authorities within 72 hours after becoming aware of the breach, and if the breach is likely to result in a high risk to data subjects, the relevant individuals will also be informed without undue delay. In addition, HUTCHMED Limited will take appropriate steps to mitigate the possible adverse effects of the data breach in coordination with the relevant parties involved in the study (whether controllers and/or processors) and those parties' data protection officers.

Data Transfer

Where applicable, personal data may be transferred to third countries outside of the European Economic Area. HUTCHMED Limited ensures the security of the data transfer by means of an Adequacy Decision, where applicable, or by concluding Standard Contractual Clauses as provided by the European Commission in adjunction with appropriate supplementary measures. A Transfer Impact Assessment will be in place before the first subject data is processed.

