APPENDIX 15 RECOMMENDATIONS FOR MANAGEMENT OF TOXICITY INCLUDING DOSE MODIFICATION

This document provides guidance to the investigators for the differential diagnosis and management of the important potential class toxicities noted on HMPL-523 trials and/or those associated with other SyK inhibitors. This constitutes general recommendations to investigators involved in HMPL-523 studies and should be supplemented with any additional protocol-specific guidance. In case of questions, prompt discussions with the sponsor's clinical representative are recommended. Please see the following tables for the dose modification and toxicity management recommendations for pulmonary toxicities, gastrointestinal toxicities such as infectious diarrhea/colitis, nausea/vomiting, hepatic AEs, infection, neutropenia, thrombocytopenia, anemia, rash and cutaneous skin reactions.

As a general principle, the recommendations are as follows:

- Differential diagnosis for any adverse event should be diligently evaluated according to standard medical practice.
- Recommendations provided here should be evaluated in conjunction with the local clinical standard of care, and overall management plan should be clearly documented and be based on the investigator's best clinical judgment.
- Consultation with specialty medical care is recommended as appropriate and especially prior to any invasive diagnostic or therapeutic procedures.
- *For events that are clearly immune-mediated, prompt initiation of steroids and gradual tapering of steroids once event has resolved is recommended.*

Table 6 Dose Modification/Toxicity Management Recommendations for Pulmonary Toxicities (Including Pneumonia/Pneumonitis)

Adverse Reaction CTCAE v5.0 Grade/Severity	Recommended Management	Recommended Dosing Modification	Recommended Followup

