
Grade 2 (Symptomatic, mild-to-moderate new or worsening symptoms)
	
 • Educate patient to report any worsening symptoms immediately • Monitor for worsening symptoms (eg, dyspnea/exertional dyspnea, cough) every 3 days or as clinically indicated • Measure SpO2 as clinically indicated • Consider empiric antibiotics while evaluating the differential diagnosis • Request pulmonary and/or infectious disease consult if cause unclear • Evaluate differential diagnosis and causality (infection/immune-related/disease progression) with standard diagnostic tests, including but not limited to the following: 
 ○ Infectious panel (consider cultures/PCR for bacterial, viral, and opportunistic infections, including PJP and CMV) ○ Chest X-ray, SpO2, and HRCT ○ PFT and BAL, as necessary ○ ILD markers (KL-6 and SP-D), if available 	
Withhold study drug
	
 • Continue close follow-up and re-imaging, as needed • If considered infectious etiology or if the etiology is unclear: 
 ○ If resolved in ≤ 7 days, resume study drug at same dose ○ If resolved in > 7 to 28 days, resume study drug at the same or a reduced dose at the discretion of the investigator 
 – If symptoms recur at the original dose, then restart study drug at a reduced dose at resolution – If symptoms recur at the reduced dose, then permanently discontinue the study drug ○ If not resolved within 28 days or worsens, consider permanently discontinuing study drug • If considered immune-related and related to study treatment, promptly start systemic steroid

Adverse Reaction CTCAE v5.0 Grade/Severity	Recommended Management	Recommended Dosing Modification	Recommended Followup

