Grade 4 Diarrhea or Colitis (Life threatening)	
 • Hospitalize and promptly start supportive treatment • Consider endoscopy and GI consult, as needed • Evaluate differential diagnosis and causality (as described above) • Prompt treatment with systemic steroids such as 1 to 2 mg/kg/day IV methylprednisolone or equivalent and/or empiric antibiotics 	Withhold study drug	
 • Continue close follow-up until resolution • Once resolved, start with reduced dose • If immune mediated, permanently discontinue study drug and promptly start steroid treatment with gradual steroid tapering • Monitor closely on restarting treatment of the diarrhea/colitis regardless of whether infectious or immune mediated; if at the reduced dose, the symptoms recur at Grade 3 or higher, then permanently discontinue the study drug

CMV = cytomegalovirus; COVID-19 = coronavirus 2019; CTCAE = Common Terminology Criteria for Adverse Events; GI = gastrointestinal; IV = intravenous; RT-PCR = real-time polymerase chain reaction.

Table 8 Dose Modification/Toxicity Management Recommendations for Hepatic Adverse Events

Adverse Reaction CTCAE v5.0 Grade/Severity	Recommended Management	Recommended Dosing Modification	Recommended Follow-up
Grade 1 or 2 AST/ALT elevation (≤5 times upper limit of the normal [ULN] or from baseline, if baseline is abnormal)	
 • Evaluate differential diagnosis and causality (including pre-existing liver disease and infectious etiology including possible COVID-19 infection [use RT-PCR for diagnosis]) • Close monitoring for worsening of any clinical signs/symptoms (eg, hyperbilirubinemia) • Close monitoring of transaminase and bilirubin levels until return to Grade 1 or < 3 times ULN • Manage with supportive care for symptom control • If the AST/ALT and bilirubin levels meet the definition of Hy's law, permanently discontinue the study drug 	Continue current dose	
 • Monitor as clinically indicated and initiate treatment as per standard of care.

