Grade 3 or 4 AST/ALT elevation (> 5 to 20 times ULN or from baseline, if baseline is abnormal)	
 • Evaluate differential diagnosis and causality (including pre-existing liver disease and infectious etiology) • Close monitoring for any clinical symptoms • Weekly monitoring of transaminase and bilirubin levels until return to Grade 1 or < 3 times ULN • Consider hepatic consult and treat accordingly per standard treatment guidelines • Permanently discontinue study drug if the patient meets the definition of Hy's law 
 ○ AST or ALT value > 3 × ULN and TBL > 2 × ULN ○ No other reason to explain combination of increased AST or ALT and TBL, ALP normal (ie, no initial findings of cholestasis) 	Withhold study drug	
 • If resolved to Grade 1 or baseline in less than 28 days, resume study drug at the same or a reduced dose at the discretion of the investigator • If not resolved to Grade 1 or baseline more than 28 days recommend restarting at a reduced dose • In case of Hy's Law or if suspicious of liver injury permanently discontinue study drug

ALP = alkaline phosphatase; ALT = alanine aminotransferase; AST = aspartate aminotransferase; COVID-19 = coronavirus 2019; CTCAE = Common Terminology Criteria for Adverse Events; RT-PCR = real-time polymerase chain reaction; TBL = total bilirubin level; ULN = upper limit of normal.

Table 9 Dose Modification/Toxicity Management Recommendations for Infection

Adverse Reaction CTCAE v5.0 Grade/Severity	Recommended Management	Recommended Dosing Modification	Recommended Follow-up
Grade 1 or 2 Infection	
 Evaluate differential diagnosis and causality (infection/immune-related/disease progression) with standard diagnostic tests (including but not limited to imaging, COVID-19 testing, chest X-ray, cultures, etc) Consider supportive care, including use of growth factors for patients with persistent or severe myelosuppression Once confirmed as infection, treat as per standard guidelines (including but not limited to antibiotics or antifungals) Consider infectious disease consult, as appropriate For patients with pulmonary or GI toxicities or myelosuppression, also refer to guidelines for management of those conditions 	Continue current dose	
 In case of persistent infection or worsening, manage as next higher grade

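### Protocol Appendix 15, Table 7: the Grade 4 diarrhea/colitis row stops study drug permanently for immune-mediated events, then gives restart rules that include them (minor)

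*Protocol*

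**What the plan says.** In Protocol Appendix 15, Table 7, the row for Grade 4 diarrhea or colitis withholds study drug and lists four follow-up bullets:

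1. Follow closely until the event resolves.
2. "Once resolved, start with reduced dose".
3. "If immune mediated, permanently discontinue study drug and promptly start steroid treatment with gradual steroid tapering".
4. "Monitor closely on restarting treatment of the diarrhea/colitis regardless of whether infectious or immune mediated"; the same bullet goes on: "if at the reduced dose, the symptoms recur at Grade 3 or higher, then permanently discontinue the study drug".

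The introduction to Appendix 15 describes its content as general recommendations, leaves the management plan to the investigator's clinical judgment and directs questions to the sponsor. For clearly immune-mediated events it advises steroids with tapering, but it does not say whether study drug may be restarted. It sets no order of precedence between bullets or tables.

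Protocol Section 5.4.2 lets the investigator resume dosing when a toxicity improves to Grade 2 or lower within 2 weeks. It makes no exception for immune-mediated events. After more than 14 consecutive days of interruption for toxicity the default is to discontinue, unless investigator and sponsor agree otherwise.

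**The concern.** Bullets 3 and 4 point in opposite directions for the same patient. A site that reads bullet 3 stops study drug for good after an immune-mediated Grade 4 event. A site that works from bullet 4 finds instructions for managing a restart after that same event, and could resume at a reduced dose. The event is life-threatening by the row's own definition, so the row should give one answer. What is at stake is the safety of the patients still on drug. No estimate or test in the SAP depends on it.

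**Working it through.** The protocol states no figure on this point, so the check compares the text and then works out the reach.

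**Step 1. Apply each bullet to an immune-mediated Grade 4 event.**

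| Bullet | Instruction | Immune-mediated events |
|---|---|---|
| 1 | Follow until resolved | Not distinguished |
| 2 | Restart at reduced dose | Not mentioned |
| 3 | Permanent stop | Named |
| 4 | Monitoring on restart; stop if Grade 3 or higher recurs at reduced dose | Named |

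**Step 2. Bullets 2 and 3.** Bullet 2 states a general rule and bullet 3 follows directly with an exception. Read in order, they are consistent.

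**Step 3. Bullets 3 and 4.** The same device does not work here. Bullet 4 names immune-mediated events, so it cannot be read as covering only the remainder left by bullet 3.

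**Step 4. Could the restarted treatment in bullet 4 be antidiarrheal therapy?** No. The second half of the bullet, "if at the reduced dose, the symptoms recur at Grade 3 or higher, then permanently discontinue the study drug", refers to the reduced dose introduced in bullet 2 and ends in stopping study drug. The restart is of study drug.

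**Step 5. Compare neighbouring rows.**

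- Table 7, Grade 3 diarrhea or Grade 2 or 3 colitis: an immune-mediated event may be followed by a reduced-dose restart. A restart-monitoring bullet fits, and that row has one, with the same Grade 3 recurrence threshold.
- Table 6, Grade 3 or 4 pulmonary events: restart and recurrence rules sit only under infectious or unclear etiology. Immune-related events get a permanent stop and no restart text.

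The Table 7 Grade 4 row has the permanent stop of the second pattern and the restart bullet of the first. A carry-over from the row above is plausible, but the documents do not say so.

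**Step 6. Reach.** Table 2 in Protocol Section 4.5 gives expansion enrollment as of Amendment 5: 25 + 1 + 7 + 2 + 2 + 1 + 1 + 9 + 0 = 48. The same section puts about 3 patients on treatment. 3 / 48 = 0.0625, or about 6%. Event counts are redacted, so the frequency of immune-mediated Grade 4 colitis cannot be estimated.

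**The case against.** **Bullet 4 orders no restart.** It sets monitoring and a further stopping rule, and grants no permission of its own. That is correct, and it is one reason the point is minor. But a rule for recurrence at the reduced dose has no use for immune-mediated events unless some of those patients restarted, and bullet 3 says none should.

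**Other provisions limit the harm.** Appendix 15 is advisory. Section 5.7.3 requires discontinuation for intolerable toxicity. Section 5.4.2 defaults to discontinuation after more than 14 days of interruption. A life-threatening event is serious under Section 6.2.2 and must reach the sponsor within 24 hours. All of this stands and bounds the consequence. None of it says which of the two bullets applies, and Section 5.4.2 would by itself permit resumption within 2 weeks.

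**Table 9 might look like a second contradiction.** For Grade 1 or 2 infection its dosing cell reads "Continue current dose", whereas Table 6 withholds for Grade 2 pulmonary events, including infectious pneumonia, and Table 7 withholds for Grade 2 colitis. A reader might infer that sites are told both to continue and to withhold. The documents do not support that reading, because the same Table 9 row says "For patients with pulmonary or GI toxicities or myelosuppression, also refer to guidelines for management of those conditions". Following that pointer leads to the organ-specific table and its instruction to withhold. What remains is that the pointer does not state which dosing cell governs, which is a matter of clarity.

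**Conclusion.** The Table 7 Grade 4 follow-up is wrong as written, and the error is minor. It comes down to one phrase in bullet 4 that contradicts the explicit stop in bullet 3. The conclusion assumes that the bullets are printed in the order extracted and that the restart in bullet 4 is of study drug (Step 4). The reach of about 6% of expansion patients uses the approximate count at Amendment 5. No endpoint, analysis or sample size changes.

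One further reading is tempting and should not be adopted. The Table 6 Grade 2 row also pairs a permanent stop with a later restart bullet that mentions immune-mediated events, and might be taken as the same contradiction. There the stop has two conditions: the event must be immune-related and also related to study treatment. The restart bullet can therefore apply to immune-related events judged unrelated to study drug. The wording is loose but has a consistent reading. Writing that reading out would create an express restart permission that the protocol nowhere states, so no edit is proposed there.

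**What to change.** In the Table 7 Grade 4 follow-up cell:

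- Keep bullet 3 unchanged.
- In bullet 4, replace the phrase beginning with *regardless* with: *for events that are not immune mediated*.
- For clarity, open bullet 2 with: *If not immune mediated,*.

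This changes two bullets in one cell. It adds no procedures and leaves the explicit stop as it is, so a clarification letter to sites should be enough.

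Optionally, add a sentence to the Table 9 row for Grade 1 or 2 infection: where Table 6 or Table 7 says to withhold (Grade 2 pneumonia, Grade 2 colitis), withhold study drug; all Table 9 stopping rules still apply. Those rules are management of persistent infection as the next higher grade, the permanent stop for infection unresolved at 28 days, and the permanent stops for CMV end-organ disease and PJP.

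The sentence should not simply declare that Tables 6 and 7 govern dosing. Table 9 carries a persistent Grade 2 infection up to the firm 28-day stop, while Table 6 Grade 2 only asks the investigator to consider stopping after 28 days. Blanket precedence could loosen the stricter rule.
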